10.1.4 Data protection

All personal data collected and/or processed in relation to this study will be handled in compliance with all applicable Privacy & Data Protection laws and regulations, including the GDPR (General Data Protection Regulation). The study Sponsor is the Sanofi company responsible for ensuring compliance with this matter, when processing data from any individual who may be included in the Sanofi databases, including Investigators, nurses, experts, service providers, Ethics Committee members, etc.

When archiving or processing personal data pertaining to the Investigator and/or to the participants, the Sponsor takes all appropriate measures to safeguard and prevent access to this data by any unauthorized third party.

Protection of participant data

Data collected must be adequate, relevant and not excessive, in relation to the purposes for which they are collected. Each category of data must be properly justified and in line with the study objective.

Participant race and ethnicity will be collected in this study because they are expected to modify the drug response/because they are required by regulatory agencies (eg, on African American population for the FDA or on Japanese population for the Pharmaceuticals and Medical Devices Agency in Japan). They will not be collected in the countries where this is prohibited by local regulation.

- Participants will be assigned a unique identifier by the Sponsor. Any participant records or datasets that are transferred to the Sponsor or its service providers will be identifiable only by the unique identifier; participant names or any information which would make the participant identifiable will not be transferred to the Sponsor.
- The participant must be informed that his/her personal study-related data will be used by the Sponsor in accordance with applicable data protection laws. The level of disclosure must also be explained to the participant as described in the informed consent.
- The participant must be informed that his/her medical records may be examined by Clinical Quality Assurance auditors or other authorized personnel appointed by the Sponsor, by appropriate IRB/IEC members, and by inspectors from regulatory authorities.
- Participants must be informed that their study-related data will be used for the whole “drug development program”, ie, for this trial as well as for the following steps necessary for the development of the investigational product, including to support negotiations with payers and publication of results.

Protection of data related to professionals involved in the study

- Personal data (eg, contact details, affiliation(s) details, job title and related professional information, role in the study, professional resume, training records) are necessary to allow Sanofi to manage involvement in the study and/or the related contractual or pre-contractual relationship. They may be communicated to any company of the Sanofi group (“Sanofi”) or to Sanofi service providers, where needed.
- Personal data can be processed for other studies and projects. At any time, objection to processing can be made by contacting the Sanofi Data Protection Officer (link available at Sanofi.com).
- In case of refusal to the processing of personal data by or on behalf of Sanofi, it will be impossible to involve the professionals in any Sanofi study. In case the professionals have already been involved in a Sanofi study, they will not be able to object to the processing of their personal data as long as they are required to be processed by applicable regulations. The same rule applies in case the professionals are listed on a regulatory agencies disqualification list.

- Personal data can be communicated to the following recipients:
 - Personnel within Sanofi or partners or service providers involved in the study.
 - Judicial, administrative and regulatory authorities, in order to comply with legal or regulatory requirements and/or to respond to specific requests or orders in the framework of judicial or administrative procedures. Contact details and identity may also be published on public websites in the interest of scientific research transparency.
- Personal data may be transferred towards entities located outside the Economic European Area, in countries where the legislation does not necessarily offer the same level of data protection or in countries not recognized by the European Commission as offering an adequate level of protection. Those transfers are safeguarded by Sanofi in accordance with the requirement of European law including, notably:
 - The standard contractual clauses of the European Commission for transfers towards our partners and service providers,
 - Sanofi's Binding Corporate Rules for intra-group transfers.
- Professionals have the possibility to lodge a complaint with Sanofi leading Supervisory Authority, the "Commission Nationale de l'Informatique et des Libertés" (CNIL) or with any competent local regulatory authority.
- Personal data of professionals will be retained by Sanofi for up to thirty (30) years, unless further retention is required by applicable regulations.
- In order to facilitate the maintenance of Investigators personal data, especially if they contribute to studies sponsored by several pharmaceuticals companies, Sanofi participates in the Shared Investigator Platform (SIP) and in the TransCelerate Investigator Registry (IR) project (<https://transceleratebiopharmainc.com/initiatives/investigator-registry/>). Therefore, personal data will be securely shared by Sanofi with other pharmaceutical company members of the TransCelerate project. This sharing allows Investigators to keep their data up-to-date once for all across pharmaceutical companies participating in the project, with the right to object to the transfer of the data to the TransCelerate project.
- Professionals have the right to request the access to and the rectification of their personal data, as well as their erasure (where applicable) by contacting the Sanofi Data Protection Officer: Sanofi DPO - [name] (to contact Sanofi by email, visit <https://www.sanofi.com/en/our-responsibility/sanofi-global-privacy-policy/contact>).

10.1.5 Committees structure

10.1.5.1 Study committee

The SC includes the Investigators or designees and Sponsor team members and, when appropriate, ad hoc experts. Decisions to continue the enrollment at a DL or to reduce the dose to be tested will be made after the appropriate data are collected and reviewed by the SC. The SC will convene regularly (eg, every 2 weeks) during Part 1 of the study (run-in); and may meet ad hoc for specific discussions. Meeting minutes will be documented.

10.1.6 Dissemination of clinical study data

Study participants

Sanofi shares information about clinical trials and results on publicly accessible websites, based on company commitments, international and local legal and regulatory requirements, and other clinical trial disclosure commitments established by pharmaceutical industry associations. These websites include clinicaltrials.gov, EU [clinicaltrialregister \(eu.ctr\)](http://clinicaltrialregister.eu), and sanofi.com, as well as some national registries.

In addition, results from clinical trials in patients are required to be submitted to peer-reviewed journals following internal company review for accuracy, fair balance and intellectual property. For those journals that request sharing of the analyzable data sets that are reported in the publication, interested researchers are directed to submit their request to clinicalstudydatarequest.com.

Individual participant data and supporting clinical documents are available for request at clinicalstudydatarequest.com. While making information available we continue to protect the privacy of participants in our clinical trials. Details on data sharing criteria and process for requesting access can be found at this web address: clinicalstudydatarequest.com.

Professionals involved in the study or in the drug development program

Sanofi may publicly disclose, and communicate to relevant authorities/institutions, the funding, including payments and transfers of value, direct or indirect, made to healthcare organizations and professionals and/or any direct or indirect advantages and/or any related information or document if required by applicable law, by regulation or by a code of conduct such as the “EFPIA Code on Disclosure of Transfers of Value from Pharmaceutical Companies to Healthcare Professionals and Healthcare Organisations”.

10.1.7 Data quality assurance

- All participant data relating to the study will be recorded on printed or electronic CRF unless transmitted to the Sponsor or designee electronically (eg, laboratory data). The Investigator is responsible for verifying that data entries are accurate and correct by physically or electronically signing the CRF.
- Guidance on completion of CRFs will be provided in the CRF completion instructions.
- The Investigator must permit study-related monitoring, audits, IRB/IEC review, and regulatory agency inspections and provide direct access to source data documents.
- Quality tolerance limits (QTLs) will be predefined in the list of predefined potential deviations to identify systematic issues that can impact participant safety and/or reliability of study results. These predefined parameters will be monitored during the study and important deviations from the QTLs and remedial actions taken will be summarized in the clinical study report.

- Monitoring details describing strategy (eg, risk-based initiatives in operations and quality such as Risk Management and Mitigation Strategies and Analytical Risk-Based Monitoring), methods, responsibilities and requirements, including handling of noncompliance issues and monitoring techniques (central, remote, or on-site monitoring) are provided in separate study documents.
- The Sponsor or designee is responsible for the data management of this study including quality checking of the data.
- The Sponsor assumes accountability for actions delegated to other individuals (eg, contract research organizations).
- Records and documents, including signed ICFs, pertaining to the conduct of this study must be retained by the Investigator for 25 years after the signature of the final study report unless local regulations or institutional policies require a longer retention period. No records may be destroyed during the retention period without the written approval of the Sponsor. No records may be transferred to another location or party without written notification to the Sponsor.

10.1.8 Source documents

- Source documents provide evidence for the existence of the participant and substantiate the integrity of the data collected. Source documents are filed at the Investigator's site.
- Data entered in the eCRF that are transcribed from source documents must be consistent with the source documents or the discrepancies must be explained. The Investigator may need to request previous medical records or transfer records, depending on the study. Also, current medical records must be available.
- Definition of what constitutes source data can be found in the eCRF completion instructions.
- The Investigator must maintain accurate documentation (source data) that supports the information entered in the eCRF.
- Study monitors will perform ongoing source data verification to confirm that data entered into the eCRF by authorized site personnel are accurate, complete, and verifiable from source documents; that the safety and rights of participants are being protected; and that the study is being conducted in accordance with the currently approved protocol and any other study agreements, ICH GCP, and all applicable regulatory requirements.

10.1.9 Study and site start and closure

First act of recruitment

The study start date is the date on which the clinical study will be open for recruitment of participants.

The first act of recruitment is the first site open and will be the study start date.

Study/Site termination

The Sponsor or designee reserves the right to close the study site or terminate the study at any time for any reason at the sole discretion of the Sponsor. Study sites will be closed upon study completion. A study site is considered closed when all required documents and study supplies have been collected and a study-site closure visit has been performed.

The Investigator may initiate study-site closure at any time, provided there is reasonable cause and sufficient notice is given in advance of the intended termination.

Reasons for study termination by the Sponsor, as well as reasons for the early closure of a study site by the Sponsor or Investigator may include but are not limited to:

- For study termination:
 - Information on the product leads to doubt as to the benefit/risk ratio
 - Discontinuation of further study intervention development
- For site termination:
 - Failure of the Investigator to comply with the protocol, the requirements of the IRB/IEC or local health authorities, the Sponsor's procedures, or GCP guidelines
 - Inadequate or no recruitment (evaluated after a reasonable amount of time) of participants by the Investigator
 - Total number of participants included earlier than expected

If the study is prematurely terminated or suspended, the Sponsor shall promptly inform the Investigators, the IECs/IRBs, the regulatory authorities, and any contract research organization(s) used in the study of the reason for termination or suspension, as specified by the applicable regulatory requirements. The Investigator shall promptly inform the participant and should assure appropriate participant therapy and/or follow-up.

10.1.10 Publication policy

- The results of this study may be published or presented at scientific meetings. If this is foreseen, the Investigator agrees to submit all manuscripts or abstracts to the Sponsor before submission. This allows the Sponsor to protect proprietary information and to provide comments.
- The Sponsor will comply with the requirements for publication of study results. In accordance with standard editorial and ethical practice, the Sponsor will generally support publication of multicenter studies only in their entirety and not as individual site data. In this case, a coordinating Investigator will be designated by mutual agreement.
- Authorship will be determined by mutual agreement and in line with International Committee of Medical Journal Editors authorship requirements.

10.2 APPENDIX 2: CLINICAL LABORATORY TESTS

- The tests detailed in [Table 10](#) will be performed by the local laboratory.
- Protocol-specific requirements for inclusion or exclusion of participants are detailed in [Section 5](#) of the protocol.
- Additional tests may be performed at any time during the study as determined necessary by the Investigator or required by local regulations.
- Pregnancy testing will be performed in all WOCBP at baseline, at End of treatment visit, and the 3 month follow-up, as detailed in the SOA ([Section 1.3](#)). Women of childbearing potential must have a negative serum pregnancy test result within 7 days prior to the initial intervention; at the End of treatment evaluation (30 ±5 days after the last IMP administration); and at the Follow-up (90 ±7 days after the last IMP administration). Additionally, during the treatment period, serum/urine pregnancy tests will be performed at the beginning of the visit every 4 weeks (ie, every 2 cycles/every other cycle).
- Investigators must document their review of each laboratory safety report.

Table 10 - Protocol-required safety laboratory assessments

Laboratory assessments	Parameters
Hematology	Platelet count
	Red blood cell (RBC) count
	Hemoglobin
	Hematocrit
	White blood cell (WBC) count with differential:
	Neutrophils
	Lymphocytes
	Monocytes
	Eosinophils
	Basophils
Clinical blood chemistry ^a	Urea/blood urea nitrogen (BUN)
	Creatinine
	Glucose
	Potassium
	Sodium
	Calcium
	Aspartate aminotransferase (AST)/Serum glutamic-oxaloacetic transaminase (SGOT)
	Alanine aminotransferase (ALT)/Serum glutamic-pyruvic transaminase (SGPT)
	Alkaline phosphatase
	Total and conjugated bilirubin
	Total protein
	Albumin
	LDH
	Coagulation

Laboratory assessments	Parameters
Urinalysis	Urine dipstick or routine urinalysis If urine dipstick or routine urinalysis indicates proteinuria $\geq 2+$, a 24 hour urine collection for protein measurement must be obtained.
Serum/urine pregnancy ^b	
Serology ^c	human immunodeficiency virus (HIV) hepatitis B virus surface antigen (HBsAg) hepatitis C virus (HCV)

Abbreviations: aPTT = activated partial thromboplastin time; ALT = alanine aminotransferase; AST = aspartate aminotransferase; BUN = blood urea nitrogen; HBsAg = hepatitis B virus surface antigen; HCV = hepatitis C virus; HIV = human immunodeficiency virus; INR = International Normalized Ratio; LDH = lactate dehydrogenase; RBC = red blood cell count; SGOT = serum glutamic-oxaloacetic transaminase (AST); SGPT = serum glutamic-pyruvic transaminase (ALT); WBC = white blood cell count.

NOTES:

- a Details of liver chemistry stopping criteria and required actions and follow-up assessments after liver stopping or monitoring event are given in Appendix 6 (Section 10.6) All events of Grade 4 AST/ALT increase must be reported as an SAE. Investigators must document their review of each laboratory safety report.
- b Only for WOCBP.
- c Serological testing for specific viral infections may not be required at all sites. Local authorities may require testing for human immunodeficiency virus (HIV), hepatitis B viral antigen (HBsAg), and/or hepatitis C virus (HCV); please refer to Appendix 8 (Section 10.8) for details of any locally required testing for these or other viruses.

10.3 APPENDIX 3: AES AND SAES: DEFINITIONS AND PROCEDURES FOR RECORDING, EVALUATING, FOLLOW-UP, AND REPORTING

10.3.1 Definition of AE

AE definition

- An AE is any untoward medical occurrence in a patient or clinical study participant, temporally associated with the use of study intervention, whether or not considered related to the study intervention.
- NOTE: An AE can therefore be any unfavorable and unintended sign (including an abnormal laboratory finding), symptom, or disease (new or exacerbated) temporally associated with the use of study intervention.

Definition of unsolicited and solicited AE

- An unsolicited adverse event is an adverse event that was not solicited using a participant diary and that is communicated by a participant who has signed the informed consent. Unsolicited AEs include serious and non-serious AEs.
- Potential unsolicited AEs may be medically attended (ie, symptoms or illnesses requiring a hospitalisation, or emergency room visit, or visit to/by a health care provider). The participant will be instructed to contact the site as soon as possible to report medically attended event(s), as well as any events that, though not medically attended, are of participant concern. Detailed information about reported unsolicited AEs will be collected by qualified site personnel and documented in the participant's records.
- Unsolicited AEs that are not medically attended nor perceived as a concern by participant will be collected during interview with participant and by review of available medical records at the next visit.

- Solicited AEs are pre-defined local and systemic events for which the participant is specifically questioned, and which are noted by the participants in their diary.

Events meeting the AE definition

- Any abnormal laboratory test results (hematology, clinical chemistry, or urinalysis) or other safety assessments (eg, ECG, radiological scans, vital signs measurements), including those that worsen from baseline, considered clinically significant in the medical and scientific judgment of the Investigator (ie, not related to progression of underlying disease), eg:
 - Leading to IMP discontinuation or modification of dosing, and/or
 - Fulfilling a seriousness criterion, and/or
 - Defined as an AESI
- Exacerbation of a chronic or intermittent pre-existing condition including either an increase in frequency and/or intensity of the condition.
- New conditions detected or diagnosed after study intervention administration even though it may have been present before the start of the study.
- Signs, symptoms, or the clinical sequelae of a suspected drug-drug interaction.
- Signs, symptoms, or the clinical sequelae of a suspected overdose of either study intervention or a concomitant medication.
- "Lack of efficacy" or "failure of expected pharmacological action" per se will not be reported as an AE or SAE. Such instances will be captured in the efficacy assessments. However, the signs, symptoms, and/or clinical sequelae resulting from lack of efficacy will be reported as AE or SAE if they fulfill the definition of an AE or SAE.
- The signs, symptoms, and/or clinical sequelae resulting from lack of efficacy will be reported as AE or SAE if they fulfill the definition of an AE or SAE. Also, "lack of efficacy" or "failure of expected pharmacological action" also constitutes an AE or SAE.

Events **NOT** meeting the AE definition

- Any clinically significant abnormal laboratory findings or other abnormal safety assessments which are associated with the underlying disease, unless judged by the Investigator to be more severe than expected for the participant's condition.
- The disease/disorder being studied or expected progression, signs, or symptoms of the disease/disorder being studied, unless more severe than expected for the participant's condition.
- Medical or surgical procedure (eg, endoscopy, appendectomy): the condition that leads to the procedure is the AE.
- Situations in which an untoward medical occurrence did not occur (social and/or convenience admission to a hospital).
- Anticipated day-to-day fluctuations of pre-existing disease(s) or condition(s) present or detected at the start of the study that do not worsen.

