2.3.1 Risk assessment

Risk assessment for tusamitamab ravtansine

Based on available safety data, the main identified risk to participants is corneal toxicity presenting as microcystic keratopathy, which is reversible and manageable with dose delay and dose reduction in some participants. Peripheral neuropathy is an identified risk in participants previously exposed to neurotoxic drugs.

Among the 16 participants in the GC cohort treated in FIH study TED13751, the most common TEAEs (reported in >10% of participants) were Asthenia (37.5%), Decreased appetite (31.3%), Fatigue (25%), Dyspnea, Nausea, Abdominal pain, Back pain, Dyspepsia, Disease progression (each in 18.8%), Anemia, Dizziness, Dry eye, Constipation, Vomiting, Ascites, and Edema peripheral (each in 12.5%).

In the loading-dose escalation phase from the FIH study, among the 28 participants treated, the most common TEAEs were: Nausea and Asthenia (each in 21.4%), Keratopathy and Abdominal pain (each in 17.9%), Peripheral sensory neuropathy, Keratitis, Dry eye, Dyspnea, and Diarrhea (each in 14.3%), and Cough, Decreased appetite, and Fatigue (each in 10.7%).

Among the 13 participants treated at the dose of 170 mg/m² at Cycle 1 followed by 100 mg/m² for subsequent cycles Q2W, preferred terms reported as TEAEs (all grades) for at least 2 participants were: Keratopathy, Keratitis, Asthenia, and Nausea (each reported for 4 participants); Decreased appetite, Peripheral sensory neuropathy, Gastroesophageal reflux disease, Proctalgia, Accidental overdose, and Dry eye (each reported for 2 participants). Grade 3 keratopathy was reported for 2 participants. No Grade 4 event was reported. Overall, the safety profile was consistent with what is reported in the main escalation phase of the study; refer to the Investigator’s Brochure for SAR408701 for details of safety data for study TED13751.

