
 To assess the safety and tolerability of tusamitamab ravtansine loading dose Q2W in combination with ramucirumab To assess the durability of the response to treatment with tusamitamab ravtansine loading dose Q2W in combination with ramucirumab To assess progression-free survival (PFS) of tusamitamab ravtansine loading dose Q2W in combination with ramucirumab To assess the disease control rate (DCR) of tusamitamab ravtansine loading dose Q2W in combination with ramucirumab To assess the pharmacokinetics (PK) of tusamitamab ravtansine loading dose Q2W and ramucirumab when given in combination To assess the immunogenicity of tusamitamab ravtansine loading dose Q2W when given in combination with ramucirumab 	
 Incidence of treatment-emergent adverse events (TEAEs), serious adverse events (SAEs), and laboratory abnormalities according to the National Cancer Institute (NCI) Common Terminology Criteria for Adverse Events (CTCAE) V5.0 Duration of response (DOR), defined as the time from first documented evidence of CR or PR until progressive disease (PD) determined per RECIST 1.1 or death from any cause, whichever occurs first Progression-free survival, defined as the time from the first investigational medicinal product (IMP) administration to the date of the first documented disease progression or death due to any cause, whichever comes first Disease control rate, defined as the proportion of participants with confirmed CR or PR or SD as BOR per RECIST 1.1 Pharmacokinetic parameters of tusamitamab ravtansine and ramucirumab Incidence of antitherapeutic antibodies (ATAs) against tusamitamab ravtansine
Exploratory	

 To explore circulating carcinoembryonic antigen (CEA) as a potential biomarker for activity and to evaluate circulating CEA levels at prescreening 	
 Circulating CEA at prescreening, screening, during the treatment period and during the follow-up period

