10.3.2 Definition of SAE

An SAE is defined as any adverse event that, at any dose:

a) Results in death

b) Is life-threatening

The term “life-threatening” in the definition of “serious” refers to an event in which the participant was at risk of death at the time of the event. It does not refer to an event, which hypothetically might have caused death, if it were more severe.

c) Requires inpatient hospitalization or prolongation of existing hospitalization

In general, hospitalization signifies that the participant has been admitted (usually involving at least an overnight stay) at the hospital or emergency ward for observation and/or treatment that would not have been appropriate in the physician’s office or outpatient setting. Complications that occur during hospitalization are AEs. If a complication prolongs hospitalization or fulfills any other serious criteria, the event is serious. When in doubt as to whether “hospitalization” occurred or was necessary, the AE should be considered serious.

Hospitalization for elective treatment of a pre-existing condition that did not worsen from baseline is not considered an AE.

d) Results in persistent or significant disability/incapacity

- The term disability means a substantial disruption of a person’s ability to conduct normal life functions.
- This definition is not intended to include experiences of relatively minor medical significance such as uncomplicated headache, nausea, vomiting, diarrhea, influenza, and accidental trauma (eg, sprained ankle) which may interfere with or prevent everyday life functions but do not constitute a substantial disruption.

e) Is a congenital anomaly/birth defect

f) Is a suspected transmission of any infectious agent via an authorized medicinal product

g) Other situations:

- Medical or scientific judgment should be exercised by the Investigator in deciding whether SAE reporting is appropriate in other situations such as significant medical events that may jeopardize the participant or may require medical or surgical intervention to prevent one of the other outcomes listed in the above definition. These events should usually be considered serious.
- Examples of such events include invasive or malignant cancers, intensive treatment in an emergency room or at home for allergic bronchospasm, blood dyscrasias or convulsions that do not result in hospitalization, or development of drug dependency or drug abuse.

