#### Analysis of all adverse events

The overview of TEAE with the details below will be generated:

- Any TEAE
- Any Grade ≥3 TEAE
- Grade 5 TEAE (any TEAE with a fatal outcome during the treatment-emergent period)

- Any treatment-emergent SAE
- Any treatment-emergent adverse event of special interest (AESI)
- Any TEAE leading to permanent full study intervention discontinuation
- Any TEAE leading to permanent partial discontinuation of tusamitamab ravtansine
- Any TEAE leading to permanent partial discontinuation of ramucirumab
- Any TEAE related to IMP
- Any Grade  $\geq$ 3 TEAE related to IMP
- Any serious TEAE related to IMP
- Any treatment-emergent corneal event (CMQ "Corneal events compound level")
- Any treatment-emergent peripheral neuropathy event TEAE (SMQ "Peripheral neuropathy" [Narrow and Broad])
- Any ocular/visual symptoms TEAE (CMQ "Eye disorders exclude corneal disorders")

The AE summaries of Table 8 will be generated with number (%) of participants experiencing at least 1 event. The analyses will be performed for all grades combined and for Grade  $\geq$ 3.

Type of AE	MedDRA levels
AII TEAE	Primary SOC, HLGT, HLT and PT
	Primary SOC and PT
	PT
TEAE related to IMP as per Investigator's judgment	Primary SOC and PT
TEAE related to tusamitamab ravtansine as per Investigator's judgment	Primary SOC and PT
TEAE related to ramucirumab as per Investigator's judgment	Primary SOC and PT
Treatment-emergent SAE	Primary SOC, HLGT, HLT and PT
	Primary SOC and PT
Treatment-emergent SAE related to IMP as per Investigator's judgment	Primary SOC and PT
Treatment-emergent SAE related to tusamitamab ravtansine as per Investigator's judgment	Primary SOC and PT
Treatment-emergent SAE related to ramucirumab as per Investigator's judgment	Primary SOC and PT
TEAE leading to permanent full study intervention discontinuation	Primary SOC and PT
TEAE leading to permanent partial discontinuation of tusamitamab ravtansine	Primary SOC and PT
TEAE leading to permanent partial discontinuation of ramucirumab	Primary SOC and PT

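### The protocol's AE definition both excludes and includes lack of efficacy, so overall TEAE, SAE and fatal-event totals can mix toxicity with inconsistently reported progression

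*Protocol*

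**What the plan says.** Protocol Section 10.3.1, in the list of events that meet the AE definition, has two adjacent bullets on lack of efficacy and failure of expected pharmacological action.

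- The first says that these "per se will not be reported as an AE or SAE. Such instances will be captured in the efficacy assessments".
- The second ends by saying that the same thing "also constitutes an AE or SAE".

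The bullets agree on one element: signs, symptoms and "clinical sequelae resulting from lack of efficacy will be reported as AE or SAE if they fulfill the definition of an AE or SAE".

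The list of events that do not meet the definition then contains a third rule: "The disease/disorder being studied or expected progression, signs, or symptoms of the disease/disorder being studied, unless more severe than expected for the participant's condition".

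This definition feeds a secondary endpoint (Protocol Section 3): "Incidence of treatment-emergent adverse events (TEAEs), serious adverse events (SAEs), and laboratory abnormalities". The SAE definition in Section 10.3.2 builds on it ("An SAE is defined as any adverse event that, at any dose") and counts death among its criteria. SAP Section 3.6.2 tabulates the AEs that sites report. I found no rule there that removes or recodes lack-of-efficacy or progression terms. The protocol's amendment history (Section 10.15) is marked not applicable, so both bullets are current text.

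**The concern.** Section 10.3.1 is the definition that sites apply when deciding whether to enter an event. A site that follows the first bullet does not enter lack of efficacy itself. A site that follows the second does, and Section 10.3.3 asks for a diagnosis rather than individual signs or symptoms wherever possible, so the entry may simply read as progression. If that entry is also serious, the 24-hour reporting duty in Section 8.3.1 depends on which bullet was followed.

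What is at stake is the meaning of the headline safety counts. Totals for participants with a TEAE, an SAE, a TEAE leading to death or a Grade 5 event could combine drug toxicity with progression recorded at some sites and not at others.

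**Working it through.** **The three rules side by side**

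| Situation | First bullet | Second bullet | Expected-progression line |
|---|---|---|---|
| Lack of efficacy in itself | Not an AE or SAE | An AE or SAE | Not addressed by name |
| Resulting symptoms or sequelae | AE if the definition is met | AE if the definition is met | Not an AE if expected for the disease |
| Progression, expected | Not an AE if read as lack of efficacy | An AE if read as lack of efficacy | Not an AE |
| Progression, more severe than expected | As above | As above | Exclusion does not apply |

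The first row is a direct contradiction. For ordinary progression the third rule supports the first bullet, but nothing states that it overrides the second. The last row shows that some progression can be reported even if the second bullet is ignored.

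**Where the ambiguity reaches the outputs**

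- *Not affected:* DLTs, because Protocol Section 6.5 excludes events due to progression; ORR, because Section 9.3.2.2 derives it from tumor assessments.
- *Partly visible:* TEAE and SAE tables by system organ class and preferred term, where a progression term has its own row; the separate tables of IMP-related events; the row for AEs leading to death in SAP Table 8, which is split by whether the context was progression; and deaths by period and reason.
- *Exposed:* the overview counts, the SAE and TEAE-leading-to-death totals, and the Grade 5 counts. The overview row "Grade 5 TEAE (any TEAE with a fatal outcome during the treatment-emergent period" is not split by cause.

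**Illustration of scale**

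The plan attaches no figure to this point, so there is none to reproduce. Inputs:

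- First-in-human gastric cohort, Protocol Section 2.3.1: 16 participants, with "Disease progression (each in 18.8" percent. This matches 3/16 = 18.75%.
- Safety population: all treated participants, up to about 38 (Protocol Sections 9.1 and 9.3.5). The planning figures give 158 × 0.30 × 0.80 = 37.9. The figure of 32 is the target for activity evaluation, not the safety denominator.

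The exact (Clopper-Pearson) 95% CI for 3/16 is 4.0% to 45.6%.

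Assuming that the same share were reported here:

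- Expected number with the term: 0.1875 × 38 = 7.1.
- Lower limit: 0.0405 × 38 = 1.5.
- Upper limit: 0.4565 × 38 = 17.3.

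These numbers describe participants carrying the term. The shift in the proportion with any TEAE would be smaller, because a participant counts once and many would have another TEAE anyway. The documents give no seriousness, grade or outcome for the three earlier events, so shifts in SAE or Grade 5 counts cannot be computed.

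**The case against.** The strongest reply is that the conflicting bullets concern lack of efficacy, whereas progression has its own line, which keeps expected progression out of the AE data. The CRF completion instructions mentioned in Protocol Section 10.1.7 may settle the matter for sites. The SAP shows progression as a separate preferred term, tabulates related events separately and splits AEs leading to death by context. The study is single-arm, tests no hypothesis and describes safety only.

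Much of this stands, and it limits the consequence. It does not remove the contradiction. The exclusion line depends on a judgement of severity and does not cancel the second bullet, the CRF instructions are not among the documents and would not correct the protocol, and the totals listed above remain unsplit.

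A reader might infer more: that about 19 percentage points of TEAE incidence hang on the choice of bullet, with no cases under the first, that the extra events would often be serious or fatal, and that a comparison with paclitaxel plus ramucirumab is thereby distorted. The documents do not support this.

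- The count under the first bullet need not be zero, since progression more severe than expected and qualifying sequelae remain reportable.
- The 18.8% comes from 16 participants with a median of 3 prior treatments (Section 2.1), in a study whose AE rules are not given here. This trial allows at most one previous line of chemotherapy (criterion I 05).
- No seriousness or outcome is reported for those events.
- Better safety than paclitaxel plus ramucirumab is given as rationale; no such comparison is planned as an analysis.

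**Conclusion.** The point holds as an internal inconsistency in current, operative text that feeds a secondary endpoint and is not resolved in the SAP. Its reach is limited to the overall TEAE, SAE, TEAE-leading-to-death and Grade 5 totals. Confidence is high for the textual conflict and lower for its practical effect, which depends on how sites have read the section. The illustrative 7 of 38 assumes that the first-in-human reporting rate carries over to a less pretreated population. It shows that the effect need not be trivial; it is neither an estimate nor an upper bound. The correction should be made, but the primary results do not depend on it.

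**What to change.** 1. **Protocol Section 10.3.1:** delete the second bullet, so that the first bullet and the expected-progression exclusion together form one reporting rule. Nothing else is lost, because the rest of the deleted bullet repeats the end of the first.
2. **CRF completion instructions:** align them with that rule.
3. **SAP Section 3.6.2:** produce the TEAE overview and the SAE, TEAE-leading-to-death and Grade 5 summaries with and without disease-progression and lack-of-efficacy preferred terms, and list those terms before database lock. This is needed because the first participant was enrolled on 21-Nov-2021 and the SAP was approved on 17-Jul-2023, so a change of text cannot correct earlier entries. The version without these terms does not depend on which sites entered them. It also leaves visible any progression legitimately reported as more severe than expected, through its difference from the full version.

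The cost is one deleted bullet, one extra set of tables and some data queries on AEs already entered.
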